11.6.2 Analysis of CSF Lab Parameters

CSF variables include RBC and WBC with differential, total protein, albumin, glucose. Summary (number of non-missing observations, minimum, mean, median, standard deviation, maximum) of mean change from baseline to Week 12 (Cohort 1 subjects only) and mean change from baseline to final double-blind value will be presented for each CSF variable.

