Lumbar punctures are required for subjects enrolled in Cohort 1 and are optional for subjects enrolled in Cohort 2. For all Cohort 1 subjects and subjects agreeing to LPs in Cohort 2, LPs to collect CSF will be performed at time points indicated in the Study Activities Table ([Appendix C](#)). Subjects will undergo a LP during Screening (preferably after all other entry criteria have been satisfied and after MRI and PET scan and any time prior to Day 1), after the 4th dose and after the final dose if administered at least 3 months after the previous LP. A sample of CSF will be collected according to the CSF Collection Manual provided to the study site by the sponsor. Computed tomography (CT)/fluoro-guided lumbar puncture can be used at the discretion of the local clinical site staff. Basic neurochemical CSF analyses will be performed locally according to the local laboratory capabilities at the applicable clinical site after each lumbar puncture/CSF collection. These measures may include cell counts (red blood cell [RBC] and white blood cell [WBC] with differential), total protein, albumin and glucose. Other CSF measurements (e.g., ABBV-8E12 concentration, tau and other exploratory biomarkers) will be analyzed by the applicable designated laboratory.

Headaches occur commonly following withdrawal of CSF. Subjects may be treated with the following, such as: IV hydration, IV caffeine administration, bed-rest and analgesics. Uncommonly a blood patch (injection of some of the subject's blood to patch the CSF leak) may be needed. Potential but rare risks of lumbar puncture include infection, damage to nerves in the back, and bleeding into the CSF space. The risk of these is much less than 1%.¹¹

COVID-19 Pandemic-Related Acceptable Protocol Modifications

In the event lumbar puncture may not be performed due to study modifications related to the COVID-19 pandemic, this procedure should be completed at the next onsite visit.

Magnetic Resonance Imaging (MRI)

For all subjects, a Magnetic Resonance Imaging (MRI) will be obtained at time points indicated in the Study Activities Table ([Appendix C](#)) and interpreted by a radiologist or neurologist. Subjects will be queried to assure they do not have specific contraindications for MRI. The Screening MRI should be completed after all other relevant screening procedures (except for the Amyloid PET and LP) have been completed and reviewed by the investigator.

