4.2 Study Design

This Phase 2 multiple dose, multicenter, multinational, randomized, double-blind, placebo-controlled study is designed to evaluate the efficacy and safety of ABBV-8E12 in subjects with Early AD. Subjects will be allowed to use medications to treat symptoms related to AD, if on a stable dose for at least 12 weeks prior to randomization. The study will consist of a screening period of up to 12 weeks, a 96-week double-blind treatment period and a follow-up period of approximately 20 weeks following the last study drug administration (for those subjects who prematurely discontinue from treatment, decline to participate in or do not qualify for extended treatment). At the end of the treatment period, eligible subjects who completed the 96-week treatment period may enter a planned separate extension study for extended treatment. All activities for these subjects will be outlined in a separate extension study protocol.

Approximately 400 subjects with Early AD between 55 to 85 years of age will be eligible to participate in the study according to the selection criteria described in protocol Section 5.2. Upon completion of screening and baseline procedures, eligible subjects will be randomized to one of the 3 ABBV-8E12 dose arms (300 mg, 1000 mg or 2000 mg) or placebo in a 1:1:1:1 ratio. Doses will be administered every 4 weeks via IV infusion.

This study will utilize a Data Monitoring Committee (DMC). The DMC will consist of at least 2 non-AbbVie clinicians, at least 1 non-AbbVie statistician and at least 1 external pharmacokineticist. The DMC will review unblinded safety data and make recommendations based on the emerging safety profile of ABBV-8E12. The DMC will review the results of the interim efficacy analyses. The DMC membership, responsibilities and operating logistics will be documented in a charter that will be finalized prior to the first DMC review meeting.

Safety and tolerability will be monitored throughout the study. The first 48 subjects enrolled into the study will be represented as Cohort 1 in this protocol while the subjects enrolled subsequently to Cohort 1 will be represented as Cohort 2. The protocol Amendment 2 states that Japanese subjects enrolled in J1 would follow safety and PK

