4.3 Sample Size

Approximately 400 Early AD subjects (100 subjects/group) will be enrolled and randomized into three ABBV-8E12 dose groups and placebo with 1:1:1:1 randomization ratio. This sample size has about 80% power to detect an ABBV-8E12 treatment effect size (vs. placebo) of 0.45 for both the high dose and the middle dose and 0.28 for the low dose on CDR-SB score changes from baseline up to Week 96 using one-sided test at the 2.5% significance level with Bonferroni method to adjust multiplicity. This power assessment was based on the assumption that 25% subjects do not have post-baseline data and the calculation was conducted using Cytel EAST version 6.4.

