6.2 Visit Definitions

Definition of Rx Day (Days Relative to the First Dose of Study Drug)

Rx Day is calculated for each time point as the number of days between the day of the first dose of study drug and the specific time point. For dates before the first dose date of study drug, Rx day = date of time point – first dose date; for dates on or after the first dose date of study drug, Rx day = date of time point – first dose date + 1. Thus, Rx Day is a negative value when the time point of interest is prior to the day of the first study drug dose; Rx Day is a positive value when the time point of interest is on or after the day of the first study drug dose. There is no Rx Day 0. With this defined algorithm, the day of the first dose of study drug will be Rx Day 1.

Rx End Day is calculated for each post-treatment time point as the number of days between the day of the last dose of study drug and the specific time point:

Rx End Day = date of time point – last dose date. With this defined algorithm, the day of the last dose of study drug will be Rx End Day 0.

Definition of Baseline and Final Observation

Unless otherwise specified, for all efficacy analyses and for all safety analyses of the double-blind Treatment Period, "baseline" shall refer to the last non-missing observation prior to the first dose of study drug and "final" for the double-blind Treatment Period shall refer to the last non-missing observation but no more than 45 days after the last dose of the study drug for both efficacy variables and safety variables. The "final" for the post-treatment follow-up period for safety variables shall refer to the last non-missing observation greater than 45 days but no more than 20 weeks after the last dose of study drug.

Randomization and study drug administration are the last activities of Day 1 Visit after the site completes other study procedures and verifies that the subject is eligible to participate in the study. From the definition of "baseline," it is clear that the baseline for a specific measurement is the last non-missing observation taken up to the Day 1 Visit (the

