An ANCOVA model will be used to evaluate CSF concentrations for total tau, free tau and the ratio of free tau concentration to total tau concentration for each scheduled time of evaluation during treatment (fourth dose interval and Week 96). For the analysis for the fourth dose interval, an analysis will be performed for the data of Cohort 1 alone and also for all available data. The observations will be classified by treatment. The baseline value for total tau and free tau (last value before the first dose of study drug) will be the covariate in the case of total tau and free tau, but for the analysis on the ratio the covariate will be the baseline total tau concentration measurement. If the probability distribution for a variable appears to have considerable non-symmetry (skewness coefficient > 0.75 in magnitude), a transformation will be sought so that the transformed variable has an approximately normal distribution. For each ABBV-8E12 dose level, the results of the test of the hypothesis of no difference between the dose and placebo will be reported. Also, with the motivation to have a test with good power if the dose response curve is a monotonic function of dose, a test will be performed on a contrast in the four treatment means. With μ_0 , μ_1 , μ_2 and μ_3 denoting the means for placebo, the 300 mg treatment, the 1000 mg treatment and 2000 mg treatment, respectively, the hypothesis that $-3\mu_0 - \mu_1 + \mu_2 + 3\mu_3 = 0$ will be tested at significance level 0.050 against the two-sided alternative hypothesis. The tests on the effects of the 1000 mg dose and the 300 mg dose will not be formally considered unless the statistic on the effect of the 2000 mg dose or the statistic on the contrast in the four means is significant at level 0.050.

CSF NFL concentration will be analyzed as described above for CSF total tau concentration. The same will be done for other CSF concentration variables for which data are reported, provided that the proportion of measurements that are outside the limits of quantification and the magnitude of the lower limit do not make a conventional analysis of covariance inappropriate.

Analysis of Serum/Plasma Concentration Variables

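### SAP 11.6.2 gives Cohort 2 no fourth-dose CSF safety-laboratory summary, and those values drop out of both planned summaries when a later on-treatment value exists

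*SAP*

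**What the plan says.** SAP 11.6.2 plans two descriptive summaries of the basic CSF laboratory variables and no test. One is the "mean change from baseline to Week 12 (Cohort 1 subjects only"; no reason is given for the limit. The other has no cohort limit: "mean change from baseline to final double-blind value will be presented for each CSF variable". SAP 6.2 defines the final double-blind value as "the last non-missing observation but no more than 45 days after the last dose of the study drug".

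Protocol 5.3.1.1 (Lumbar Puncture) makes punctures mandatory in Cohort 1 and optional in Cohort 2. Footnote r to the study activities table (Protocol Appendix C, SAP Table 2) gives the Cohort 2 time points as screening, Week 12 and Week 96. The basic CSF tests are run "at the applicable clinical site after each lumbar puncture/CSF collection", without distinction by cohort. They depend on what the local laboratory can do, and the protocol says only that they may include the variables the SAP lists.

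For CSF tau and NFL in the fourth dose interval, SAP 13.0 says "an analysis will be performed for the data of Cohort 1 alone and also for all available data". Protocol 8.1.7.1 likewise summarises CSF drug concentration for Cohort 1 and for all subjects.

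**The concern.** One puncture yields three kinds of data: biomarkers, drug concentration and safety laboratory values. The first two are summarised for everyone who had the puncture. Only the safety values are confined to Cohort 1. CSF cell count and protein bear directly on central nervous system safety, long-term safety is a primary objective, and Cohort 2 subjects give these samples through an invasive optional procedure.

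At stake is the precision of an early, time-specific CSF safety summary. An early change that had resolved by a later puncture would also not be visible in Cohort 2 in either planned summary.

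**Working it through.** **Inputs.** Total N is about 400 (SAP 4.3: "Approximately 400 Early AD subjects (100 subjects/group) will be enrolled"). Cohort 1 is 48 (SAP 4.2: "The first 48 subjects enrolled into the study will be represented as Cohort 1"). Allocation is to three doses or "placebo in a 1:1:1:1 ratio", that is, four arms.

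**Check of the arithmetic.** 400/4 = 100 per group, as SAP 4.3 states. The plan gives no per-arm number for CSF laboratory values, so there is no other figure to reproduce.

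**Per-arm numbers.**
- Cohort 1: 48/4 = 12. This is an expectation. Randomization is stratified by site only, so the split of the first 48 is not fixed, and missed punctures or missing baselines lower it.
- Cohort 2: (400 − 48)/4 = 352/4 = 88, of whom an unstated share has punctures.

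**Where a Cohort 2 subject's values go under SAP 11.6.2 and 6.2.**

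| CSF values available | Week 12 summary | Final-value summary | Fourth-dose value used? |
|---|---|---|---|
| Baseline, fourth dose | excluded | fourth-dose value | yes, pooled with Week 96 values |
| Baseline, fourth dose, later on-treatment | excluded | later value | no |
| Baseline, later on-treatment only | excluded | later value | none to use |

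So no Cohort 2 subject with a baseline and an on-treatment value is left out of the analysis. What is lost is the fourth-dose value in the second row. In the first row the value is kept, but it is mixed with values taken after up to 24 doses.

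**Possible size, under assumption.** Let u be the share of Cohort 2 with both a baseline and a fourth-dose CSF result, and v the share of those with a later on-treatment result. The documents give neither. An all-available-data summary at the fourth dose would have n = 12 + 88u per arm. The standard error of a mean change, in units of a common SD, is 1/√n. The values absent from both current summaries number 352 × u × v over all arms.

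| u (assumed) | n per arm | 1/√n | Values in neither summary (v from 0 to 1) |
|---|---|---|---|
| 0 | 12 | 0.289 | 0 |
| 10% | 20.8 | 0.219 | 0 to 35 |
| 25% | 34 | 0.171 | 0 to 88 |
| 50% | 56 | 0.134 | 0 to 176 |
| 100% | 100 | 0.100 | 0 to 352 |

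The last row is an upper bound, not an expectation.

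**The label.** Dose 4 is on Day 85 and the puncture follows about 14 days later: 85 + 14 = Day 99, about Week 14. Protocol 5.3.1.2 calls this sample Week 14; SAP 11.6.2 and footnote r call it Week 12. SAP 6.2 has no window for CSF. If its clinical-laboratory windows were applied, Week 12 ends on Rx Day 98 and Week 16 starts on Rx Day 99, so a puncture made on its target day would be assigned to Week 16.

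**The case against.** A reader might infer from the Week 12 restriction that CSF safety is examined in only about 12 subjects per arm, and that adding Cohort 2 would greatly raise the chance of seeing an abnormal case. The documents do not support this, for three reasons.

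- The final-value summary has no cohort limit, so the extra subjects in such a comparison are already in it.
- The planned tables describe change from baseline and do not count abnormal subjects, so a probability of seeing at least one case does not measure what they show.
- Individual abnormal values have other routes in both cohorts. CSF basic tests are in Protocol Table 3, and Protocol 5.3.1.1 (Abnormal Findings) has the investigator judge clinical significance and decide on adverse event reporting. SAP 11.2 summarises adverse events by treatment group. Protocol 5.5.5 gives the DMC full access to data needed for safety assessment, and SAP 4.4 includes Cohort 2 in the mandatory safety reviews.

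Nor can it be said that identical tests are done at every Cohort 2 puncture, given the local-capability wording. All of this stands and limits the point.

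The restriction can also be defended: Cohort 1 is the intensively monitored cohort with mandatory punctures, whereas Cohort 2 is self-selected. That is a reason to keep the Cohort 1 table, not to omit a second one. It could be added that the parallel with SAP 13.0 is imperfect, because tau goes to a designated laboratory and the basic tests are run locally. But the basic tests are local in Cohort 1 too, so this does not justify a split by cohort.

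**Conclusion.** The point holds in a limited form. The fourth-dose CSF safety summary is restricted to Cohort 1 without a stated reason and out of line with the other CSF analyses of the same puncture. Cohort 2 values at that puncture have no time-point summary, and they appear in neither summary when a later on-treatment value exists. The figure of about 12 per arm describes the Week 12 summary only, not the CSF safety analysis as a whole.

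The size of the loss depends on Cohort 2 uptake and on local testing, neither of which the documents give; the tabulated range is illustrative. The severity is minor: the summary is descriptive, carries no test and affects no primary or multiplicity-controlled conclusion.

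**What to change.** In SAP 11.6.2, summarise change from baseline to the fourth-dose puncture by treatment group, once for Cohort 1 alone and once for all available data, as SAP 13.0 does for CSF tau and NFL. Keep the final-value summary as it is. Report the number of subjects contributing to each table, since uptake and local testing will vary.

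In the same edit, reconcile the Week 12 label with the puncture about 14 days after Dose 4, and state which results count as the fourth-dose value, because SAP 6.2 has no CSF window.

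The cost is a change of wording and one repeated descriptive table. The one drawback is that Cohort 2 subjects are self-selected; the separate Cohort 1 table lets a reader see whether that matters.

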11.6.3 Summary of MRI Safety Evaluations

MRI safety evaluations will be summarized and compared between each ABBV-8E12 dose and placebo based on MRI evaluations in the double-blinded period. The summaries include number and percentage of subjects with presence and severity of baseline and post baseline MRI findings of cerebral edema, microhemorrhages, and severe white matter disease as defined by a score of 3 on Age-Related White Matter Changes (ARWMC) scale and other structural abnormalities. Descriptive statistics (mean, median, minimum, maximum) of number of new microhemorrhages or new lesions in the double-blind period will be presented. Listing of subjects with post-baseline MRI findings will be provided. No comparison will be performed for MRI safety summary.

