The Screening MRI assessment will rule out the presence of any intracranial masses that might preclude the subject from undergoing a lumbar puncture and exclude focal or diffuse processes that could interfere with the diagnosis of AD or MCI, including signal abnormalities on FLAIR or T2 weighted images consistent with infectious, vascular, neoplastic or other degenerative processes. The 3D T1 weighted sequences will also be acquired for volumetric analysis that will enable a quantitative assessment of the whole and regional brain volume.

On-treatment safety MRI analysis will be performed at the time points indicated in the Study Activities Table. On-treatment volumetric MRI analysis will be performed at the time points indicated in the Study Activities Table ([Appendix C](#)) starting from Week 28.

The MRI scan should be done prior to the LP otherwise at least a 3-day window between the LP and the MRI appointment is necessary. Details of the MRI procedures will be described in the MRI Procedures Manual provided by the Sponsor.

COVID-19 Pandemic-Related Acceptable Protocol Modifications

In the event MRI may not be performed due to study modifications related to the COVID-19 pandemic, this procedure should be completed at the next onsite visit.

Positron Emission Tomography (PET) Amyloid Imaging

For all subjects without an acceptable historical amyloid positive PET scan, an amyloid PET scan will be obtained at Screening. The acceptability of the historical PET scan will

be determined by the central reader. Even though amyloid is not a target for ABBV-8E12, amyloid imaging is included for subject selection to increase the diagnostic and prognostic accuracy in the early stages of AD. It allows for a better differential diagnosis of cognitive impairment and identification of individuals that are at increased risk of progressive cognitive decline.

Subjects will be queried to assure they do not have specific contraindications for PET such as a history of radiation therapy within the past year, or a history of receiving radiation for research purposes within the past year. The amyloid PET scan should be completed after all other relevant screening procedures including screening MRI scan have been completed and reviewed by the investigator.

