If a subject is discontinued from the study with an ongoing adverse event or an unresolved laboratory result that is significantly outside of the reference range, the investigator will attempt to provide follow-up until a satisfactory clinical resolution of the laboratory result or adverse event is achieved.

COVID-19 Pandemic-Related Acceptable Protocol Modifications

Subjects who miss multiple study drug doses due to the COVID-19 pandemic may continue participation with approval from the TA MD.

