8.1.6 Safety Analyses

All safety analysis will be performed on the safety data set unless otherwise specified. Comparisons between each ABBV-8E12 dose group and placebo will be performed with two-sided test at the significance level of 0.05, if applicable. Pairwise comparisons for each ABBV-8E12 dose group versus placebo will be evaluated.

All safety assessments that are taken no more than 20 weeks after the last dose of study drug will be included in the safety evaluation for subjects who complete the double-blind Treatment Period or PD and do not roll over to the planned extension study. If subjects enroll in the planned extension study, their safety information collected before the first dose of the planned extension study will be included in the safety evaluation for the double-blinded period.

Study Drug Exposure and Compliance

The number of doses on study drug will be summarized by treatment group and all treatment groups combined. The number and percentage of subjects with at least 90% compliance with study drug (i.e., complete 90% of scheduled doses) will be summarized by treatment group and all treatment groups combined.

Adverse Events

A treatment-emergent adverse event (TEAE) is defined as any adverse event that begins or worsens in severity on or after the first study drug dose date and no more than 20 weeks after the last study drug dose date.

Unless otherwise specified, the treatment group differences in continuous safety variables (e.g., change from baseline to final observation on laboratory tests) will be assessed using an ANOVA model with the term of treatment, and the treatment group differences in binary safety variables will be evaluated using a Fisher's exact test.

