	Day 365 ^c	Day 393 ^c	Day 421 ^c	Day 449 ^c	Day 477 ^c	Day 505 ^c	Day 533 ^c	Day 561 ^c	Day 589 ^c	Day 617 ^c	Day 645 ^c	Day 673 ^c	Days 729	Day 785
ADA Sample ^k						X						X	X	X
Diagnostic Tools and Rating Scale ^{m,q}						X						X		
Columbia Suicide Severity Rating Scale	X	X	X	X	X	X	X	X	X	X	X	X	X	
Concomitant Medication Review	X	X	X	X	X	X	X	X	X	X	X	X	X	X
Adverse Event Monitoring ⁿ	X	X	X	X	X	X	X	X	X	X	X	X	X	X

C1 – Cohort 1 subjects only, Procedures should be conducted at approximately the same time as they would be conducted on the days of dosing.

- Visits on Days 5, 15, 89 and 99 must be scheduled within ± 2 days of the scheduled date. Visits on all other days may be scheduled within ± 4 days of the scheduled date.
- Post-Treatment Visits to occur approximately 8 and 16 weeks after the Completion or Premature Discontinuation (PD) visit.
- Assessments on Day -7 to -1 will be done once during this time frame and can be administered on any day, but all should be done on the same day. Assessments may also be completed on Day 1, but must be completed prior to the start of the study drug infusion. At visits after Day 1 rating scales may be completed on any day within the visit window prior to the visit, but all rating scales should be completed on the same day.
- Only subjects enrolled in Cohort 1 will be required to return to the clinical site 5 and 15 days after doses 1 and 4.
- Height collected at Screening Visit 1 only. On dosing days, weight will be collected prior to the start of the infusion.
- A detailed description for the timing of 12-Lead Single ECGs can be found in Section 5.3.1.1 in the protocol.

Table 2. Study Activities (Continued)

- g. Randomization should be completed just prior to the first dose administration.
- h. The MRI will be scheduled approximately 2 weeks following the dose and results must be available prior to the next scheduled dose.
- i. The lumbar puncture will be performed approximately 14 days after the fourth dose.
- j. The optional Pharmacogenetic DNA and RNA samples require consent. Verify consent prior to sample collection.
- k. A detailed description of the collection time points can be found in Section 5.3.2.1 in the protocol.
- l. ADA sample for Cohort 1 will only be collected on Day 15.
- m. See [Table 3](#) for additional information on Diagnostic Tools and Rating Scales.
- n. A detailed description for procedures involving adverse event assessments can be found in Section 6.0 in the protocol.

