- Week 16 Rx Day 99 through 126
- Week 20 Rx Days 127 through 154
- Week 24 Rx Days 155 through 210
- Week 36 Rx Days 211 through 294
- Week 48 Rx Days 295 through 378
- Week 60 Rx Days 379 through 462
- Week 72 Rx Days 463 through 546
- Week 84 Rx Days 547 through 630
- Week 96 Rx Days > 630

For measurements that are planned to be collected during the double-blind treatment period at Weeks 2, 4, 8, 12, 24, 36, 48, 72 and 96, i.e., ECG, observation will be mapped to an analysis "week" according to the following windows defined by Rx day.

- Week 2 Rx Days 2 through 21 (Cohort 1 subjects)
- Week 4 Rx Days 22 through 42 (Cohort 1 subjects)
Rx Days 2 through 42 (Cohort 2 subjects)
- Week 8 Rx Days 43 through 70
- Week 12 Rx Days 71 through 126
- Week 24 Rx Days 127 through 210
- Week 36 Rx Days 211 through 294
- Week 48 Rx Days 295 through 420
- Week 72 Rx Days 421 through 588
- Week 96 Rx Days > 588

For vital sign measurements, C-SSRS, ECG, clinical laboratory tests, and MRI that are planned to be collected during the post-treatment follow-up period at Weeks 104, observations will be mapped to an analysis "week" according to the following windows defined by Rx End day.

- Post-Treatment Week 8 Rx End Days > 45

For measurements that are planned to be collected during double-blind treatment period on Weeks 6, 14, 30, 46, 70 and 96, i.e., MRI observation will be mapped to an analysis "week" according to the following windows defined by Rx day.

- Week 6 Rx Days 2 through 70
- Week 14 Rx Days 71 through 154
- Week 30 Rx Days 155 through 266
- Week 46 Rx Days 267 through 406
- Week 70 Rx Days 407 through 581

- Week 96 Rx Days > 581

If more than 1 observation is included in a visit time window, the observation that is closest to the nominal day of the visit will be used in the analysis. If two observations have the same distance to the nominal day of the visit, the last non-missing observation will be used in analyses. If more than 1 observation occurs on the same day, the average will be calculated and used in analyses.

7.0 Demographics, Baseline Characteristics, Subject History, and Previous/Concomitant Medications

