11.0 Safety Analysis

11.1 General Considerations

All safety analyses will be performed on the safety dataset. Unless otherwise specified, treatment group differences in safety parameters are evaluated using two-sided test at the significance level of 0.050. When statistical tests are performed, the comparisons will be between each ABBV-8E12 dose and placebo. With the exception of adverse events, all safety assessments that are taken no more than 45 days after the last dose of study drug infusion will be included in the safety evaluation of the Double-blind Treatment Period. All safety assessments that are taken more than 45 days but no more than 20 weeks after the last dose of study drug infusion will be included in the safety evaluation for the Post-Treatment Follow-Up Period.

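### The MRI safety tables stop 45 days after the last dose, so a late Week 96 scan reaches only the listing, and only if it shows a finding

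*SAP*

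**What the plan says.** SAP 11.6.3 is the only section that specifies MRI safety output. Findings (edema, microhemorrhage, severe white matter disease, other structural abnormalities) are to be counted by arm and "compared between each ABBV-8E12 dose and placebo based on MRI evaluations in the double-blinded period". The descriptive statistics on new microhemorrhages and lesions carry the same limit. The section also asks for a listing of subjects with findings after baseline, without a period limit.

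For safety data other than adverse events, SAP 6.2 and 11.1 end the double-blind period 45 days after the last dose; 6.2 applies this by default. For what follows, SAP 11.1 takes "All safety assessments that are taken more than 45 days but no more than 20 weeks after the last dose of study drug infusion" and assigns them to the post-treatment follow-up evaluation. SAP 6.2 gives MRI a window there, "Post-Treatment Week 8 Rx End Days > 45", together with vital signs, C-SSRS, ECG and laboratory tests.

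Protocol 8.1.6 draws the lines differently. For subjects who do not enter the extension, assessments taken "no more than 20 weeks after the last dose of study drug will be included in the safety evaluation". For those who do, "their safety information collected before the first dose of the planned extension study will be included in the safety evaluation" of the double-blind period.

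Two protocol provisions make late scans foreseeable. "In the event MRI may not be performed due to study modifications related to the COVID-19 pandemic", Protocol 5.3.1.1 moves the scan to the next onsite visit. Protocol 5.4.1 adds: "Subjects who miss multiple study drug doses due to the COVID-19 pandemic may continue participation with approval from the TA MD".

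**The concern.** MRI has a defined window after day 45 and no table that uses it. The other measures named in that window do have a specified output that reaches past day 45: laboratory tests, vital signs and ECG have a change from final double-blind to final post-treatment value (SAP 11.3.1, 11.4.1, 11.5.1), and C-SSRS is summarized for the entire study (SAP 11.6.1).

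The listing does not fill the gap. It covers subjects with findings, so a clean scan after day 45 appears in no MRI safety output, and there is no by-arm denominator for late scans.

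For a subject who reaches Week 96, the Week 96 scan is the only scheduled MRI after the one at about Week 70. If it falls past the cut, a lesion first seen on it is absent from the by-arm counts. Long-term safety up to 96 weeks is a primary objective, so those counts should reflect scans that were actually taken.

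**Working it through.** **Inputs.** Dosing is every 4 weeks for 24 infusions, so dose n falls on Day 1 + 28(n − 1). This reproduces the schedule (Protocol Appendix C, SAP Table 2): dose 18 = Day 477, dose 19 = 505, dose 22 = 589, dose 23 = 617, dose 24 = 645. Week 96 is Day 673 and Week 104 is Day 729. Visits have a window of ±4 days. SAP 6.2 defines Rx End Day as the assessment date minus the last dose date. The cut is 45 days.

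**Gap from last dose to an on-time Week 96 scan.** The range puts ±4 days on both the dose and the scan.

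| Case | Nominal gap | Range | In the table? |
|---|---|---|---|
| All 24 doses given | 673 − 645 = 28 | 669 − 649 = 20 to 677 − 641 = 36 | Yes |
| Dose 24 missed | 673 − 617 = 56 | 669 − 621 = 48 to 677 − 613 = 64 | No |
| Doses 23 and 24 missed | 673 − 589 = 84 | 669 − 593 = 76 to 677 − 585 = 92 | No |

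**All doses given, Week 96 scan deferred.** The last day inside the cut is 645 + 45 = Day 690, which is 690 − 673 = 17 days after nominal Week 96. With dose 24 given on Day 641 to 649, the limit is Day 686 to 694, or 13 to 21 days late. A scan moved to Week 104 would be at 729 − 645 = 84 days; that visit applies only to subjects who do not enter the extension.

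**What the table then lacks.** On the scan after dose 18, SAP Table 2 says: "The MRI will be scheduled approximately 2 weeks following the dose and results must be available prior to the next scheduled dose". It is therefore at about Day 477 + 14 = 491, before dose 19 and 673 − 491 = 182 days before Week 96. Infusions with no later scheduled scan in the counts:

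- dose 24 missed: doses 19 to 23, so 5;
- doses 23 and 24 missed: doses 19 to 22, so 4;
- all given, scan deferred past the cut: doses 19 to 24, so 6.

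**Also affected:** a premature-discontinuation or unscheduled scan more than 45 days after the last dose.

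**Not affected:** a discontinuation scan at the visit where the next dose would have been given (28 days, range 20 to 36), and a dose missed mid-study with dosing resumed, because the cut runs from the last dose.

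**Against the protocol.** Take a rollover subject scanned at 56 days, before the first extension dose. Under Protocol 8.1.6 that scan belongs to the double-blind evaluation; under SAP 11.1 it does not. SAP 14.0 does not itemize this change. For other subjects, SAP 11.1 keeps the protocol's 20-week span and divides it in two; what is missing is an MRI table for the second part.

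**The case against.** The strongest reply is that the SAP already assigns these scans: 6.2 names MRI in the post-treatment window and 11.1 sends later assessments to the follow-up evaluation, so all that is missing is a table for a defined window. That is right as a description, and a reader who infers that late scans are excluded from the safety evaluation goes too far. But 11.6.3 is where the tables are specified, and it names only the double-blind period.

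Second, SAP 6.2 counts Week 96 among the MRI times of the double-blind period, with an open-ended window (Rx Days > 581). A Week 96 scan at 56 days fits that window and the post-treatment one. The overlap is real. The 45-day rule is still the likelier reading, because 6.2 applies it unless otherwise specified and 11.6.3 specifies nothing else.

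Third, MRI is not singled out for its counts: the potentially clinically significant counts for laboratory tests, vital signs and ECG are also double-blind only, with a listing. This stands.

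Fourth, the information is kept elsewhere. The listing holds late findings, a finding reported as an adverse event counts as treatment-emergent up to 20 weeks, Protocol 5.4.1 has treatment-emergent MRI findings reported to the sponsor's medical director, and the DMC reviews unblinded safety data. This limits the harm.

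A reader might also infer a bias in favor of the drug, or a conflict with Protocol 8.1.6 for every subject. Neither is supported. Nothing in the documents gives a direction between arms, and the conflict is firm only for subjects who enter the extension.

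**Conclusion.** The point holds and is minor. On the likelier reading, MRI scans more than 45 days after the last dose enter no by-arm MRI safety count, and a clean one appears in no MRI safety output. A Week 96 scan after a missed dose 24 is past the cut at every point of the visit windows (48 to 64 days). With full dosing, a Week 96 scan is past it once deferred by more than about 17 days (13 to 21). In the cases worked, 4 to 6 infusions then have no later scheduled scan in the table.

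This rests on the 45-day default governing 11.6.3 despite the overlapping Week 96 window. Only subjects with missed final doses or late scans are affected, and the documents do not allow their number to be derived. No inference changes: although 11.6.3 opens by speaking of a comparison, it closes by ruling one out.

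**What to change.** In SAP 11.6.3, add a column by arm for MRI findings and new lesions on any post-baseline scan up to 20 weeks after the last dose or, for rollover subjects, before the first extension dose. Use the number of subjects scanned in that span as the denominator, and show the column beside the 45-day one. This also brings the rollover rule of Protocol 8.1.6 into the MRI table.

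The cost is a sentence or two and one table column, with no new data. The downside is unequal follow-up: subjects scanned later have longer to show a finding. The 45-day column should therefore stay for comparison.
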